10. Patients who have congestive heart failure (NYHA Class III or IV), unstable angina, sustained ventricular tachycardia, ventricular fibrillation, clinically significant bradycardia, advanced heart block or a history of acute myocardial infarction within the six months preceding enrollment
11. QT related exclusion criteria
 - QTcF at screening > 470 msec.
 - History of syncope or family history of idiopathic sudden death.
 - Sustained or clinically significant cardiac arrhythmias.
 - Risk factors for Torsades de Pointes such as hypokalemia, hypomagnesemia, cardiac failure, clinically significant/symptomatic bradycardia, or high-grade AV block.
 - Concomitant disease(s) that could prolong QT such as autonomic neuropathy (caused by diabetes, or Parkinson's disease), HIV, cirrhosis, uncontrolled hypothyroidism or cardiac failure
 - Concomitant medication(s) known to increase the QT interval.
12. Patients with the presence of active or suspected acute or chronic uncontrolled infection or with a history of immunocompromise, including a positive HIV test result (ELISA and Western blot).
13. Patients who have any severe and/or uncontrolled medical conditions or other conditions that could affect their participation in the study such as:
 - Severely impaired lung function (as defined as spirometry and DLCO that is 50% of the normal predicted value and/or O₂ saturation that is 88% or less at rest on room air)
 - Any active (acute or chronic) or uncontrolled infection/ disorders.
 - Nonmalignant medical illnesses that are uncontrolled or whose control may be jeopardized by the treatment with the study therapy
 - Impairment of gastrointestinal function or gastrointestinal disease that may significantly alter the absorption of RAD001
 - Patients who have a history of drug abuse in the 6 month period prior to receiving treatment with pasireotide or RAD001
 - History of, or current alcohol misuse/abuse within the past 12 months
 - Acute or chronic pancreatitis
14. Women who are pregnant or breast feeding, or women/men of reproductive potential who are not using and unwilling to practice an effective method of birth control. (Women of childbearing potential must have a negative serum pregnancy test within 7 days prior to administration of pasireotide and RAD001).
15. Male patient whose sexual partner(s) are WOCBP who are not willing to use adequate contraception, during the study and for 8 weeks after the end of treatment
16. Patients with a known hypersensitivity to RAD001 (everolimus) or other rapamycins (sirolimus, temsirolimus) or to its excipients
17. Known hypersensitivity to somatostatin analogues or any component of the pasireotide or octreotide LAR formulations
18. History of noncompliance to medical regimens

19. Patients unwilling to or unable to comply with the protocol
20. Patients taking medications known to be strong CYP3A inhibitors (Table 6-5).

6 Treatment

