Interim PK analysis has shown that a steady state appeared to be achieved following three monthly i.m. injections of 20 mg (N=5), 40 mg (N=7) or 60 mg (N=8) pasireotide LAR in carcinoid patients. The mean (SD) concentration versus time profiles of pasireotide are shown in [Figure 1-2](#). The median (mean \pm SD) trough plasma concentrations of pasireotide on days 28, 56 and 84 are shown in [Table 1-3](#). The release pattern of pasireotide from the first injection of 40 and 60 mg LAR in carcinoid patients ([Figure 1-2](#)) was very similar to that of a single-dose of 40 and 60 mg LAR in healthy volunteers. PK exposures to pasireotide on day 84 at steady state in carcinoid patients ([Table 1-3](#)) were roughly 2-fold higher than the simulated concentrations at steady state following multiple doses in healthy volunteers ([Section 1.3.2.1](#)).

Figure 1 Error! No text of specified style in document.-2 **Mean (SD) plasma concentration versus time profiles of pasireotide in carcinoid patients following three monthly i.m. injections of 20 mg (N=5), 40 mg (N=7), or 60 mg (N=8) pasireotide LAR [CSOM230C2110]**

Source: [SOM230C2110]

Table 1-5 **Median (Mean plus or minus SD) trough plasma concentrations of pasireotide on days 28, 56 and 84 in carcinoid patients following three monthly i.m. injections of 20 mg (N=5), 40 mg (N=7) or 60 mg (N=8) pasireotide LAR [CSOM230C2110]**

Dose (mg)	Day 28 (ng/mL)	Day 56 (ng/mL)	Day 84 (ng/mL)
20 (N=5)	2.7 (N=2)	5.7 (N=1)	6.9 (N=1)
40 (N=7)	7.2 (10.6 ± 8.2) (N=6)	5.9 (13.8 ± 16.8) (N=3)	12.0 (17.7 ± 10.5) (N=3)
60 (N=8)	14.2 (15.6 ± 9.2) (N=8)	28.2 (28.5 ± 7.8) (N=4)	16.9 (16.2 ± 4.8) (N=4)

Source: [SOM230C2110]

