RAD001 is rapidly absorbed with a median t_{max} of 1-2 hours. The bioavailability of the drug is believed to be 11% or greater. The $AUC_{0-\tau}$ is dose-proportional over the dose range between 5 to 70 mg in the weekly regimen and 5 and 10 mg in the daily regimen. C_{max} is dose-proportional between 5 and 10 mg for both the weekly and daily regimens. At doses of 20 mg/week and higher, the increase in C_{max} is less than dose-proportional. The coefficient of variation between patients is approximately 50%.

Trough levels (24 hour post-dose) correlate well with $AUC_{0-\tau}$ at steady-state during daily administration.

In whole blood, at a daily dose of 10 mg, about 20% of RAD001 is confined in plasma with 26% being unbound. The remaining 80% is sequestered in blood cells.

RAD001 is extensively metabolized in the liver and eliminated in the bile. Major metabolites are inactive. Elimination half-life is approximately 30 hours. The clearance of RAD001 is approximately halved in patients with mild-moderate hepatic impairment (Child-Pugh Class A or B), while renal impairment has little or no impact on the pharmacokinetics of RAD001.

Age, weight and gender in the adult population do not affect the pharmacokinetics of RAD001 to a clinically relevant extent. The clearance of RAD001 is reduced in children.

Pharmacokinetic characteristics are not notably different between Caucasian and Japanese subjects, whereas in Black patients population pharmacokinetic studies have shown an average 20% higher clearance.

A high-fat meal altered the absorption of RAD001 with 1.3 hour delay in t_{max} , a 60% reduction in C_{max} and a 16% reduction in AUC.

RAD001 is a substrate of CYP3A4 and a substrate and a moderate inhibitor of the multi-drug efflux pump P-glycoprotein (P-gP, MDR1, ABCB1). Hence, its metabolism is sensitive to drugs which modify these enzymes (substrates, inducers, or inhibitors of these enzymes). Competitive inhibition could occur when RAD001 is combined with drugs which are also CYP3A4 or P-glycoprotein substrates

Table 6-9 (Section 6-8) lists examples of clinically relevant CYP3A inhibitors and inducers.

Please refer to [Section 6-8](#) for more information on the concomitant use of CYP3A4 inhibitors/inducers and other medications.

More information on RAD001 pharmacokinetics is provided in the [\[Investigator's Brochure\]](#).

RAD001 Pharmacodynamic studies

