13. Women of childbearing potential must have a negative serum pregnancy test within 7 days of the administration of the first study treatment. Women must not be lactating. Both men and

women of childbearing potential must be advised of the importance of using effective birth control measures during the course of the study.

14. Signed informed consent to participate in the study must be obtained from patients after they have been fully informed of the nature and potential risks by the investigator (or his/her designee) with the aid of written information.
15. INR and PTT $\leq 1.5 \times$ ULN. (Anticoagulation is allowed if target INR ≤ 1.5 on a stable dose of warfarin or on a stable dose of LMW heparin for >2 weeks at time of randomization.)

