6.3 Treatment arms

Arm A: Everolimus 10 mg daily continuously (switch to 2-drug combination at progression if no intolerable toxicity)

Arm A1: Patient switching from single agent everolimus to 2-drug combination will be re-registered as Arm A1

Arm B: Pasireotide LAR 60mg i.m. once every 4 weeks (switch to 2-drug combination at progression if no intolerable toxicity)

Arm B1: Patient switching from pasireotide LAR single agent to 2-drug combination will be re-registered as Arm B1

Arm C: Everolimus 10 mg daily continuously together with Pasireotide LAR 60mg i.m. once every 4 weeks

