 - The results of the ECGs, cardiac examination, Holter-ECGs and the recommendation by the cardiologist must be evaluated by the investigator to determine whether the patient should continue in the trial or not (discontinuation criteria to be followed).
- **C_{max} drug concentration visit:** If at a Day 21 visit (day 21 after any injection of Pasireotide/Octreotide LAR) a C_{max} QTcF>480 msec is observed for the first time for a patient at a given dose level, the following steps need to be taken:
 - A cardiology consultation as described in the preceding section must be sought as soon as practicable but within 7 days after the initial abnormal ECG and prior to the next Pasireotide/Octreotide LAR injection.
 - All steps described in the preceding section must be followed, however if a Holter ECG is required, a 24hour Holter ECG must be recorded when the patient receives the next scheduled Pasireotide/ Octreotide LAR injection. The Holter ECG should be started 30min prior to the injection.
- **Trough concentration visit e.g. day 1 of a new cycle:** If at any visit a trough level QTcF>480 msec is observed for the first time for a patient at a given dose level, the following steps need to be taken:
 - A cardiology consultation as described in the preceding section must be sought as soon as practicable but within 7 days after the initial abnormal ECG and prior to the next Pasireotide/Octreotide LAR injection.
 - All steps described in the preceding section must be followed; however if a Holter-ECG is required, a 24hour Holter-ECG must be recorded and evaluated prior to the next injection of Pasireotide/Octreotide LAR. The Pasireotide/Octreotide injection must be postponed until the Holter-ECG results are available with a maximal permissible delay of 7 days. If the outcome of the cardiac evaluation is that the patient may receive a further dose of Pasireotide/Octreotide LAR, then a second 24hr Holter-ECG must be done on the day of the LAR injection.

- This Holter ECG should be started 30min prior to the injection.

Table 6-8a: Guidelines for dose modification for QT prolongation while on SOM230

Adverse event	Action
*Grade ≤ 2	No study drug adjustments

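### Men have a stated 8-week post-treatment contraception period; the available eligibility text ties no such period to a woman's own last dose, which matters mainly for women given pasireotide LAR

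*Combined protocol and SAP*

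**What the plan says.** Three eligibility lines deal with contraception.

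- Section 5.1, inclusion 13, addresses both sexes: "women of childbearing potential must be advised of the importance of using effective birth control measures during the course of the study". It is a duty to advise, and it does not say when the study ends for this purpose.
- Section 5.2, exclusion 14, keeps out "women/men of reproductive potential who are not using and unwilling to practice an effective method of birth control". It gives no duration.
- Section 5.2, exclusion 15, applies only to male patients with partners of childbearing potential. It requires contraception "during the study and for 8 weeks after the end of treatment".

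The other pregnancy-related text covers testing (Table 7-1, at screening and Cycle 1 Day 1 only), withdrawal of drug (7.5.5) and reporting (7.5.1.1, 7.5.1.3, 7.5.5). None of it sets a contraception period. Section 6.7 follows patients for adverse events for 28 days after the last dose. Section 4.2 continues survival contact, at least monthly, until death or trial completion at LPLV + 30 days (LPLV read here as last patient, last visit).

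**The concern.** The sex that would carry a pregnancy has the less definite rule. A man can work out from exclusion 15 when his obligation ends, and a woman cannot do so from inclusion 13 or exclusion 14. Pasireotide LAR is a monthly depot, so exposure continues for weeks after the last injection. Table 7-1 schedules no pregnancy test after Cycle 1 Day 1, so contraception is the main planned safeguard from then on. What is at stake is possible drug exposure in an unplanned pregnancy soon after treatment stops. Response rate, PFS and the choice of a winning arm are not involved.

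**Working it through.** There is no design figure to reproduce. The check compares the text, then sets the available exposure data beside it.

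**1. The lines side by side**

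| Line | Applies to | Period stated |
|---|---|---|
| Inclusion 13 | men and women | while the study runs; end not defined |
| Exclusion 14 | men and women | none |
| Exclusion 15 | men with partners of childbearing potential | the study, plus 8 weeks after treatment ends |

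The lines do not conflict. Men are already under inclusion 13 and exclusion 14, yet exclusion 15 names the study period and then adds 8 weeks after treatment. The study-period wording was therefore not relied on to cover the time after treatment for men, and it does not clearly do so for women.

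**2. How long a woman is covered under each reading**

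The men's period is 8 × 7 = 56 days. Let d be the days from a woman's last dose to LPLV.

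| Reading of the study period | Days after last dose | Shortfall against 56 |
|---|---|---|
| Ends with her own treatment | 0 | 56 |
| Ends with her 28-day adverse event follow-up | 28 | 56 − 28 = 28 |
| Ends at LPLV + 30 days | d + 30 | 26 − d if d < 26, otherwise none |

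On the widest reading only women whose last dose falls within 26 days of LPLV are short. Enrolment is planned over 30 months (Figure 4-1), so most would be covered. The text does not say which reading applies.

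**3. Pasireotide exposure**

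Section 6.7 places the C_max visit 21 days after a LAR injection. Table 1-5 (section 1.3) samples on days 28, 56 and 84 of a monthly schedule, so each value is 28 days after the latest injection, or 28 − 21 = 7 days after the time of the C_max visit.

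| Dose | Day 28 median, ng/mL (N) | Day 56 | Day 84 |
|---|---|---|---|
| 60 mg | 14.2 (8) | 28.2 (4) | 16.9 (4) |
| 40 mg | 7.2 (6) | 5.9 (3) | 12.0 (3) |
| 20 mg | 2.7 (2) | 5.7 (1) | 6.9 (1) |

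These are interim values from small numbers of carcinoid patients. For scale, section 1.3 estimates about 10 ng/mL for symptom control in carcinoid disease. The table shows exposure to at least 28 days after an injection. For the remaining 56 − 28 = 28 days of an 8-week period the documents give no level.

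**4. Everolimus alone**

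Section 1.4: "Elimination half-life is approximately 30 hours". Five half-lives are 5 × 30 = 150 hours = 6.25 days, leaving 1/32, or about 3%. The depot argument does not carry over.

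**The case against.** **Unavailable text.** Section 11.2 makes the consent form part of the protocol. The consent pages, and text between sections 7.5.1.3 and 7.5.2, were not available. Either could hold a period for women. This stands: a reader might infer that the protocol has no post-treatment period for women, and the documents do not support that. Only the available text can be described.

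**The study continues after the last dose.** A reader might infer that a woman may stop contraception at her last injection. That is too strong. Adverse event follow-up, the end-of-study and follow-up visits, and monthly contact all come later, and exclusion 14 has no end date that releases her. What remains is that none of these is a contraception rule counted from her last dose.

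**The exposure data stop at the dosing interval.** Days 21 and 28 lie inside the last 4-week cycle, where drug is expected. A reader might infer exposure up to week 8, or a known fetal risk. The documents give no level later than 28 days after an injection and no embryo-fetal data for pasireotide, so neither follows.

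**A male-specific reason is possible.** Section 1.4 reports animal toxicity with everolimus that was at least partly reversible within weeks, except for changes in male reproductive organs. That could partly explain exclusion 15. The protocol does not give this as its reason, and it would not be a reason to leave directly exposed women without a defined period.

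**Pregnancy reporting is not a gap of any size.** Section 7.5.5 requires each pregnancy to be reported. Section 7.5.1.1 treats a birth defect as serious and keeps it reportable after 4 weeks if causality is suspected.

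**Conclusion.** The point holds in a limited form. The available eligibility text gives men 8 weeks after treatment and gives women no period counted from their own last dose. The possible shortfall for a woman runs from none to 56 days, depending on an undefined phrase; under the reading that extends to LPLV + 30 days it is at most 26 days and affects only the last patients. The concern applies mainly to women who receive pasireotide LAR (Arms B, C, A1 and B1). For women on everolimus alone it rests on consistency with exclusion 15, which does not distinguish between arms.

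The conclusion assumes that the consent form and the unavailable text do not already set a period. The number of women of childbearing potential is not given, so the number affected cannot be estimated. Severity is minor and confides itself to patient safety.

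**What to change.** First check the consent form and the Investigator's Brochures for a stated period. Then amend inclusion 13 and exclusion 14 so that women of childbearing potential use effective contraception during treatment and for at least 8 weeks after the last dose of study drug, or longer if the Investigator's Brochure requires it. Keep the consent form consistent with the amended lines.

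The 8 weeks is taken from exclusion 15 for consistency; it is not derived from the exposure data in the protocol. One rule for all arms is simplest because Arm A patients may later receive the depot: "Patient switching from single agent everolimus to 2-drug combination will be re-registered as Arm A1" (section 6.3).

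The cost is wording in two eligibility lines and a consent check. The at-least-monthly contact in section 4.2 can carry a reminder and a pregnancy question. The downside is a slightly longer contraception commitment, with weak exposure support for women who only ever receive everolimus.

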6.1 Investigational and control drugs

Known undesirable effects of study drug/treatment

For information on Pasireotide and Everolimus, please refer to Section 1, Human experience, and the Investigator Brochure.

6.2 Study drugs

SOM230C

Study drug: pasireotide LAR (long-acting release) i.m. depot injection

Inactive ingredients of pasireotide LAR include: mannitol, carmellose sodium (carboxymethylcellulose sodium), poloxamer 188 and water for injection. Inactive ingredients of pasireotide s.c. include: mannitol, tartaric acid, sodium hydroxide and water for injection.

For detailed information on pasireotide, please refer to Sections 1.3 and 1.4 or the pasireotide Investigator Brochures.

How supplied

Study drug, Pasireotide LAR i.m. depot injections will be supplied in open-label packaging by Novartis as a powder in vials containing 20 mg and 40 mg labeled as SOM230 LAR, with ampoules containing 2 mL of vehicle (for reconstitution). No syringes or needles will be provided with the pasireotide study drug supplies.

Preparation and storage

Prior to reconstitution, vials should be brought to room temperature. Pasireotide LAR should then be prepared as follows:

Table 6-1 Handling and preparation of pasireotide LAR dose

Dose	Volume to be injected
20 mg	1 x 20 mg vial + 2 mL vehicle; whole volume to be injected
40 mg	1 x 40 mg vial + 2 mL vehicle; whole volume to be injected
60 mg	1 x 20 mg vial + 1 x 40 mg vial + 2 mL vehicle; whole volume to be injected

Doses should be prepared and administered immediately after preparation.

Novartis will supply pasireotide LAR as long as the patient remains on study, shows continuous benefit from treatment, and there are no safety concerns. Medication labels will

comply with the legal requirements of the U.S. and will be printed in English. The storage conditions for pasireotide LAR will be described on the medication label. Bottles must be stored in a safe, secure location.

All study medication will be supplied to each site directly by Novartis. Under the responsibility of each site's lead investigator, drug supplies must be kept in an appropriate, secure area (e.g. locked cabinet) and stored in accordance with the conditions specified on the drug labels. The investigator must maintain an accurate record of the shipment and dispensing of the study drug in a drug accountability ledger. An accurate record of the date and amount of study drug dispensed to each subject must be available for inspection at any time.

All drug supplies are to be used only for this protocol and not for any other purpose. Unless specifically instructed by Novartis, the investigator must not destroy any drug labels, or any unused drug supply.

The storage condition for the study drug will be described on the medication label.

Administration

Pasireotide LAR will be administered i.m., intragluteally, every 4 weeks. The starting dose will be 60 mg. The reconstitution has to be performed just prior to administration of the suspension. A minimal standing time can be tolerated for the reconstituted suspension in the vial. Prior to administration, the reconstituted suspension in the vial should be shaken again before withdrawal in the syringe. The i.m. injection must be given immediately after withdrawal of the reconstituted suspension from the vial to the syringe.

RAD001 Administration

The study drug RAD001 will be self-administered (by the patients themselves). The investigator will instruct the patient to take the study drug exactly as specified in the protocol. RAD001 will be administered orally as once daily dose of 10 mg continuously from study day 1 until progression of disease or unacceptable toxicity. Patients will be instructed to take RAD001 in the morning, at the same time each day.

RAD001 may be taken by the patient with or without food. However, dietary habits around the time of RAD001 intake should be as consistent as possible throughout the study.

If vomiting occurs, no attempt should be made to replace the vomited dose.

All dosages prescribed and dispensed to the patient and all dose changes during the study must be recorded.

Medication labels will comply with US legal requirements and be printed in English. They will supply no information about the patient. The storage conditions for study drug will be described on the medication label.

RAD001 will be provided by Novartis. RAD001 is formulated as tablets for oral administration of 2.5mg, 5mg and 10mg strengths. Tablets are blister-packed under aluminum foil in units of 10 tablets, which should be opened only at the time of administration as drug is both hygroscopic and light-sensitive.

6.3 Treatment arms

Arm A: Everolimus 10 mg daily continuously (switch to 2-drug combination at progression if no intolerable toxicity)

Arm A1: Patient switching from single agent everolimus to 2-drug combination will be re-registered as Arm A1

Arm B: Pasireotide LAR 60mg i.m. once every 4 weeks (switch to 2-drug combination at progression if no intolerable toxicity)

Arm B1: Patient switching from pasireotide LAR single agent to 2-drug combination will be re-registered as Arm B1

Arm C: Everolimus 10 mg daily continuously together with Pasireotide LAR 60mg i.m. once every 4 weeks

